8.9.2.2 Demographic and Baseline Characteristic

Summary of demographic and baseline variable described in [section 8.4.1](#) and [8.4.2](#).

8.9.2.3 Summary and analysis of NRS score

The change from baseline in the weekly mean of the 24-hour Worst Itching Intensity NRS score at each post baseline week of the treatment period will be summarized. Treatment differences between CR845 and placebo at each post baseline time point will be evaluated and presented using mixed effects model with repeated measures (MMRM). Refer to [section 8.6.2](#) for the details of NRS data analysis.

Summary statistics will be provided for the observed and the change from baseline with respect to the weekly mean of the 24-hour Worst Itching Intensity NRS score by strata- renal disease status (moderate CKD non-dialysis; severe CKD non-dialysis; and severe CKD on dialysis).

Statistical Analysis Plan (SAP)

8.9.2.4 Summary and analysis of Skindex-10 and 5-D Itch total scale score and Responder Analysis

The secondary efficacy endpoints mentioned below will be summarized for IA.

- Change from baseline in itch-related quality of life at the end of Week 12, as assessed by the total Skindex-10 Scale score;
- Change from baseline in itch-related quality of life at the end of Week 12, as assessed by the total 5-D Itch Scale score;
- Proportion of patients achieving an improvement from baseline ≥ 3 points with respect to the weekly mean of the daily 24-hour Worst Itching Intensity NRS score at Week 12 of the Treatment Period.

Refer to [section 8.6.3](#) for details of the analysis for the above endpoints.

8.9.2.5 Safety Analysis

The following summaries will be provided to evaluate the safety profile of CR845. Analysis details are provided in [section 8.7.1](#). Except for the first display listed below, only TEAE during treatment period will be summarized.

- Overall summary of Adverse Event
- AEs summary by SOC and PT
- AEs related to study drug by SOC and PT
- AEs leads to study drug discontinuation by SOC and PT
- AEs by Maximum severity
- Serious adverse event summary
- Summary of Clinically important laboratory values
- Summary of Sodium abnormal findings (<146 mmol/L, ≥ 146 mmol/L, ≤ 150 mmol/L, >150 mmol/L)

Line plot for the below parameters will also be provided.

- Change from baseline in selected Laboratory Tests over Time (hemoglobin, creatinine, GFR, albumin, phosphate, calcium, sodium)
- Blood Pressure Measurements (Systolic and diastolic blood pressure)
- Heart Rate Measurements

In addition, the following listings will also be provided to support safety data.

- Listing of Adverse Events
- Listing of death
- Listing of Serious Adverse Events
- AEs leading to study drug discontinuation
- Listings for clinically important laboratory values

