4.3 Summary of Potential Risks and Benefits

The potential benefit of CR845 in alleviating the symptoms of pruritus associated with chronic kidney disease (CKD) in hemodialysis patients is predicated on its pharmacological class and evidence of its effectiveness in multiple animal models of pruritus and in two Phase 2 clinical studies with IV CR845 in hemodialysis patients experiencing moderate-to-severe pruritus (CR845-CLIN2005 Part B and CR845-CLIN2101).

In humans with normal renal function, CR845 has aquaesthetic effects that can result in dehydration and associated symptoms (eg, tachycardia) and hypernatremia if the fluid balance is not managed properly. However, these effects appear to be absent in the dialysis population, many of whom are anuric and all of whom have few functioning nephrons. These effects are also anticipated to be largely reduced in CKD patients stage III to IV not yet on dialysis.

Overall, tingling/numbness, dizziness, fatigue and/or drowsiness/somnolence have been the most common adverse events. Due to the potential adverse event of fatigue/drowsiness/somnolence, subjects should be cautioned about operating hazardous machinery or operating a motor vehicle.

Gastrointestinal dysfunction (abdominal discomfort, nausea, constipation) may be possible, as it has been frequently reported after oral tablet administration in normal healthy volunteers.

Tingling sensation or facial numbness has been reported shortly after administration of CR845. This effect is transient and does not appear to be a clinically significant issue.

While it has been demonstrated that CR845 has substantially less access to the CNS than previously tested kappa opioid agonists, adverse CNS effects of CR845 (eg, altered mental status) could still be considered a possibility (eg, hypothetically, in patients with impaired blood-brain barrier functioning).

A detailed summary of the potential risks and benefits of CR845 is provided in the [\[Investigator's Brochure\]](#). The Investigator must become familiar with all sections of the current Investigator's Brochure for CR845 before the start of the study.

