6.5.2.3 Vital Signs

Vital signs include sitting or semi-recumbent body temperature, heart rate, and blood pressure.

Measurements will be repeated if a value is out of the reference range due to a technical issue, considered abnormal for the patient, or for other medical concerns. Only the repeated measurement will be recorded.

In the event of a clinically significant change in blood pressure and/or heart rate, the Investigator and staff will evaluate and manage the patient per standard practices with knowledge of the patient's typical blood pressure and heart rate excursions.

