3.2 Randomization and blinding

Before the start of the study, a computer-generated randomization schedule will be prepared. Randomization will be performed using an interactive voice or web response system (IVRS/IWRS). Patients will be randomized in a 1:1:1:1 ratio to receive either placebo or CR845 tablets at doses of 0.25, 0.5, or 1 mg. Randomization will be stratified according to the patient's renal disease status: moderate CKD non-dialysis; severe CKD non-dialysis; severe CKD on dialysis (ie, 3 categories). The randomization of severe CKD patients on hemodialysis will be capped at approximately 20% of the total sample size (ie, 48 of 240 patients).

Patients, investigators, study staff, and the sponsor will be blinded to study drug assignment. For medically urgent or emergent situations that necessitate knowledge of study drug assignment for patient management, the blind may be broken via the IVRS/IWRS. Whenever possible, the medical monitor should be contacted prior to breaking the blind. The sponsor and medical monitor will receive a report whenever a patient blind is broken.

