8.7.3 Vital signs

Vital sign parameters include systolic blood pressure (SBP), diastolic blood pressure (DBP), body temperature and heart rate. For each scheduled timepoint, descriptive summary statistics will be calculated for both the actual and the change from baseline values for all

Statistical Analysis Plan (SAP)

vital sign parameters. The baseline value is defined as the last observation prior to or on the date of the first dose of study drug whether scheduled or unscheduled (see [section 7.1](#)).

Clinically notable vital signs will be identified based on the criteria below. For each vital sign parameter, the number and percentage of subjects with at least 1 notable value will be tabulated by week and overall for Treatment period. This analysis will include results from both scheduled and unscheduled assessments.

Vital Sign Parameter	Value
Systolic blood pressure	≥ 180 mm Hg
	≤ 90 mm Hg
Diastolic blood pressure	≥ 100 mm Hg
	≤ 60 mm Hg
Heart rate	>130 bpm
	<55 bpm

All vital signs will be listed in patient listings, including visit and collection date/time, and will be sorted by patient identifier and date/time of assessment.

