8.9 Interim analysis

An unblinded Interim Analysis (IA) will be conducted when approximately 50-60% of the planned 240 patients have been randomized and have either completed the 12-week Treatment Period or have discontinued study drug early. The primary goal of the IA is to identify dose(s) of oral CR845 that are both safe and efficacious across all strata. Doses that are found to be unsafe or poorly tolerated will be dropped from the study. No dose will be dropped for futility reasons. The sample size will not be increased past 480 total patients (120 patients per treatment group).

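### The interim safety list shows blood pressure and heart rate only as line plots; the vital-sign outputs already specified in SAP 8.7.3 should be added to it

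*SAP*

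**What the plan says.** SAP 8.9 makes the interim analysis the planned point for acting on safety dose by dose: "Doses that are found to be unsafe or poorly tolerated will be dropped from the study". It is held when "approximately 50-60% of the planned 240 patients have been randomized" and have either completed or stopped treatment.

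SAP 8.9.2.5 lists the safety outputs for that review. Adverse events get several tables and listings. Laboratory values get a table of clinically important values, a sodium category table, a plot of change from baseline and a listing. Vital signs appear once, under the line "Line plot for the below parameters will also be provided", with one entry for heart rate and one for "Blood Pressure Measurements (Systolic and diastolic blood pressure". Both entries name measurements; unlike the laboratory entry, neither says change from baseline. For analysis details the section points to 8.7.1 (adverse events), not to 8.7.3 (vital signs).

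SAP 8.7.3 specifies two fuller outputs:

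- Descriptive statistics of observed values and of change from baseline at each scheduled time point. Under SAP 8.1, such summaries include the minimum and maximum.
- A notable-value table, in which "the number and percentage of subjects with at least 1 notable value will be tabulated by week and overall for Treatment period", with unscheduled readings included. The limits are absolute: systolic at or below 90 or at or above 180 mm Hg, diastolic at or below 60 or at or above 100 mm Hg, heart rate below 55 or above 130 bpm.

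Protocol 4.3 says that in people with normal renal function the drug's effect on fluid balance "can result in dehydration and associated symptoms (eg, tachycardia) and hypernatremia". It adds that these effects appear absent in dialysis patients and are expected to be much smaller in stage III to IV patients not on dialysis.

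**The concern.** The interim review decides whether a dose continues. Under SAP 8.9.1 any sample size increase applies to all treatment groups, up to 120 patients each, so a dose with an unseen problem could be enlarged because another dose looks promising.

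The fluid-balance risk has two sides, sodium and hemodynamics. The interim list tabulates sodium by category but gives no patient-level display of blood pressure or heart rate. If only a few patients in an arm react strongly, a plot of group means is a weak tool for finding them. The plan already describes better tools and does not list them for the interim.

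The adverse event route is also less explicit for vital signs than for ECGs. Protocol 6.5.2.4 has clinically significant ECG findings after the first dose reported as treatment-emergent adverse events. Protocol 6.5.2.3 has no such sentence: "In the event of a clinically significant change in blood pressure and/or heart rate, the Investigator and staff will evaluate and manage the patient".

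**Working it through.** The plan gives no figure for vital signs, so there is none to reproduce. The calculation asks what a plot of means could show and what the 8.7.3 table would count.

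**Interim size.** From "approximately 50-60% of the planned 240 patients have been randomized" and "Patients will be randomized in a 1:1:1:1 ratio to receive either placebo or CR845 tablets at doses of 0.25, 0.5, or 1 mg": 0.50 × 240 / 4 = 30 and 0.60 × 240 / 4 = 36 patients per arm.

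**What a mean can show.** Assumptions, none of them in the documents: 10% of one arm changes by a fixed amount and the rest do not; the between-patient SD is 20 mm Hg (systolic) or 12 bpm (heart rate).

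- Shift in arm mean = proportion affected × change.
- SE of the difference between two arms = SD × √(2/n).

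| Scenario | Shift in mean | SE, n = 30 | SE, n = 36 | Shift / SE |
|---|---|---|---|---|
| Systolic fall of 40 in 10%, SD 20 | 0.10 × 40 = 4 mm Hg | 5.2 | 4.7 | 0.8 |
| Same, SD 15 | 4 mm Hg | 3.9 | 3.5 | 1.0–1.1 |
| Same, SD 10 | 4 mm Hg | 2.6 | 2.4 | 1.5–1.7 |
| Heart rate rise of 30 in 10%, SD 12 | 0.10 × 30 = 3 bpm | 3.1 | 2.8 | 1.0–1.1 |

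In the first and last rows the chance that a two-sided 5% comparison of means is significant is 12–14% and 16–19%. If 5% are affected instead of 10%, the shift in those two rows is about 0.4 to 0.5 SE. Even with an SD of 10 the systolic shift stays below 1.96 SE.

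**What the notable-value table would count.** Its limits are absolute, so the starting value matters. Further assumptions: baseline means of 130–150 mm Hg and 70–80 bpm, the same SDs, normal distributions, and no variation other than the change itself.

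- A 40 mm Hg fall reaches 90 only from a baseline at or below 130. That is Φ((130 − 150)/20) = 16% to Φ(0) = 50% of affected patients.
- A 30 bpm rise exceeds 130 only from a baseline above 100. That is 1 − Φ((100 − 70)/12) = 0.6% to 1 − Φ((100 − 80)/12) = 5% of affected patients.

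With 10% of an arm affected, the expected number counted is 0.5 (30 × 0.10 × 0.16) to 1.8 (36 × 0.10 × 0.50) for systolic pressure. For heart rate it is 0.02 to 0.17. The chance of counting at least 2 such patients is 8–54% for systolic pressure and about 1% or less for heart rate.

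The table alone is therefore not enough. A change-from-baseline summary with minimum and maximum does not depend on the starting level and shows the most extreme individual change.

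**The case against.** **Adverse events.** Protocol 6.5.2.1.1 counts any new sign or symptom, and any new clinically significant or symptomatic test abnormality, as an adverse event. Marked hypotension or tachycardia of that kind would ordinarily be reported and would appear in the interim adverse event tables and listing. This stands. A reader might infer that the interim review could not see such a signal at all; the documents do not support that. What remains is changes that are asymptomatic, or that the investigator does not judge significant or does not report, because this route does not apply the SAP's own limits.

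**Content of the plots.** The SAP says line plots, not mean plots. SAP 1 puts display templates in a separate document, and the Protocol synopsis says the same of interim details; neither is available here. This also stands, so the loss of individual changes is conditional on the plots showing means. But SAP 1 states that it covers the interim analysis, and its interim list contains no other vital-sign output.

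**Stakes.** Protocol 4.3 expects the fluid-balance effect to be absent or reduced in this population, and sodium and creatinine have interim displays. Protocol 6.3.2 lets the sponsor stop part of the study at any time, and Protocol 6.5.2.1.7 requires SAE reports within 24 hours. A reader might take the interim as the only safeguard. It is the planned dose-dropping point, not the only protection. On the other side, the reduction in non-dialysis patients is an expectation, and dialysis patients are capped at about 20% of the sample.

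**The notable-value table as remedy.** Since 10% of 30 is 3, a reader might infer that the table would show about 3 of 30 patients in the scenarios above. It would not, because it counts values beyond a limit and not changes.

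**Conclusion.** The omission is plain on the text: the interim list gives vital signs less than it gives laboratory values, and less than SAP 8.7.3 specifies. If the plots show means, a 40 mm Hg fall in 10% of an arm amounts to 0.8 SE under an SD of 20 mm Hg (up to 1.7 SE under an SD of 10), and a 30 bpm rise in 10% to about 1 SE under an SD of 12 bpm. Differences of that size are hard to tell from noise at 30 to 36 patients per arm.

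The SDs, baseline means, affected proportions and sizes of change are all assumptions. The gap is limited to unreported or asymptomatic changes, and the documents do not show that an unsafe dose would be missed. This is a cheap improvement to the evidence behind a dose-dropping decision; no sample size or power figure changes.

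**What to change.** Add to the list in SAP 8.9.2.5, by treatment group:

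1. The 8.7.3 table of patients with at least 1 notable value, from scheduled and unscheduled readings.
2. The 8.7.3 change-from-baseline summary for blood pressure and heart rate, with minimum and maximum.
3. A listing of patients with a notable value.

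Point the section to 8.7.3 for details. Items 1 and 2 belong together: the table counts patients beyond the limits, and the summary shows large changes that stay within them, though only the most extreme ones and not how many. Neither can recover a first reading that was replaced, since Protocol 6.5.2.3 records only the repeated measurement.

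The cost is two or three more interim outputs. The first two are already specified; whether they have been programmed is not stated. The change needs no new limit and no dose-dropping rule.

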9 CHANGES TO PLANNED ANALYSIS FROM STUDY PROTOCOL

- Antipruritic medications are not identified in the CRF or the database using a Yes/No flag. The use of antipruritic medications will need to be derived based on the indication entered on the CRF. Therefore, a specific analysis of antipruritic medications by ingredient will not be completed since it will not be different than the analysis summarizing medications by preferred term.
- Section 8.6.1 of the protocol defines the primary endpoint as follows: “The weekly mean of the 24-hour Worst Itching Intensity NRS score will be defined as the sum of the daily Worst Itching Intensity NRS score reported during a specific week during the Treatment Period (eg, Days 2 to 8, Days 9 to 15, Days 16 to 22, etc.) divided by the number of days with non-missing scores for that week. If the daily worst itching score is missing for >3 days during a specific week, the corresponding weekly mean worst itching score will be set to missing.”. However, to facilitate patient diary dates anomalies which may result in duplicate dates (e.g. patient completes diary shortly after midnight and then again on same date) and the fact that only the diary date is used for mapping to a specific week as per [section 7.1](#), of this SAP, the underlined text above is replaced with “...divided by the number of non-missing scores for that week. If there are <4 non-missing daily worst itching scores during a specific week...”. In addition, because in this study the Day 1 NRS score is planned to be taken after dosing, weeks are re-defined in this SAP one day earlier than stated in the protocol (eg. Days 1 to 7, Days 8 to 14, Days 15 to 21, etc.).
- Section 8.6.2 of the protocol states that missing Skindex-10 Itch Scale and 5-D Itch Scale total scores will not be imputed. To ensure a more unbiased assessment of these secondary endpoints, which does not ignore missing data, analyses in this SAP state that the same MI method with MAR assumption will be applied to these endpoints in similar fashion to the primary endpoint.
- Section 8.6.3 of the protocol stated that the study would be considered positive if the null hypothesis of no treatment difference is rejected in favor of the alternative that patients randomized to CR845 experience significantly less itching as measured by the change from baseline in the weekly mean of the Worst Itching Intensity score at Week 12. In fact, since this study compares several CR845 doses versus placebo, the study will be considered positive if at least one dose is found to be safe and effective. Effectiveness will be evaluated based on results of the primary efficacy analysis either using the estimate of treatment effect or the p-value of the hypothesis tests.

Statistical Analysis Plan (SAP)

